#### 2.7.1.3 Analysis

The following summaries will be provided (within 30 days; within 365 days):

- a. Overall summary of AEs
- b. All AEs by primary SOC and PT
- c. AEs suspected to be related to procedure and/or device by primary SOC and PT
- d. Serious adverse events (SAEs) by primary SOC and PT
- e. SAEs suspected to be related to procedure and/or device by primary SOC and PT
- f. AEs leading to discontinuation by primary SOC and PT
- g. Most frequent AEs (5% or 10%) by primary SOC and PT
- h. Bleeding Events
- i. Major Bleeding Events (within 72 hours; within 30 days; within 365 days)
- j. VTE (DVT and PE)
- k. diagnosis of pulmonary hypertension
- 1. composite measure of recurrent symptomatic PE, PE related death or hemodynamic collapse at 30 days
- m. Death resulting from AEs by primary SOC and PT

In addition, the following summaries will also be provided by subgroups described in section 2.2.1.

- Overall summary of AEs
- All AEs by primary SOC and PT
- SAEs by primary SOC and PT
- Most frequency AEs (5% or 10%) by primary SOC and PT

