### 3. SCHEDULE OF REGISTRY ASSESSMENTS – PROSPECTIVE

Assessments will be performed per Investigator's SoC and collected according to the schedule below. Assessments marked with an asterisk (\*) pertain to an outcome measure or eligibility.

Assessment	Baseline	Procedure/Post Procedure	Follow-up	
	Day -1	Day 0 thru Discharge	3 Months (±14 Days) Post APT (Phone or Visit)	12 Months (±1 Month) Post APT (Phone or Visit)
Informed Consent	X*			
Demographics	X*			
Medical history, risk factors	X*			
Vital signs 	X*	X		
Physical Examination	X			
CTA	X*	X*  (if collected)		
sPESI	X			
APT Procedure		X		
Echocardiogram 	X*	X  (if collected)	X* (if collected)	X* (if collected)
Quality of life surveys 		X*	X*	X*
Laboratory tests 	X 	X		
Biomarkers 	X*	X		
Adverse/VTE/Bleeding Events		X*	X*	X*
Anticoagulation medications	X	X	X	X

1. Record heart rate, blood pressure, respiratory rate, oxygen saturation vital signs at admission, at start and end of treatment, and once at same time each day of hospitalization  
 2. Includes RV/LV ratio, TAPSE, estimated RVSP, and collapse of the inferior vena cava (IVC) with respiration  
 3. Collect 24 – 48 hours after the start of the APT procedure  
 4. PEmb-QOL and EQ-5D-5L  
 5. Hemoglobin (Hgb), hematocrit (Hct), platelet count, creatinine, activated partial thromboplastin time (aPTT), partial thromboplastin time (PT), and international normalized ratio (INR)  
 6. Record if collected within 48 hours prior to the start of APT procedure  
 7. Troponin, brain natriuretic peptide (BNP)/NT-proBNP, lactate/lactic acid, and D-dimer

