### 5.3 Outcome Measures

---

1. Change in the ratio of the measurement of the RV/LV diameters as measured by echocardiogram or CTA from baseline to between 24 – 48 hours after the start of the APT procedure (matched pairs as available).
2. Diagnosis of pulmonary hypertension defined as mean pulmonary artery pressure greater than 25 mm Hg by echocardiogram that persists at least 3 months after PE diagnosis
3. Frequency and safety outcomes of adjunctive therapies post APT procedure during hospitalization
4. Number of patients with non or partial response to other interventional procedures prior to APT procedure for index PE
5. Frequency and severity of SAEs related to EKOS and procedure, major bleeding, or VTE during index hospitalization and during first 12 months post-APT procedure
6. All-cause mortality during first 12 months post-APT procedure
7. Recurrent symptomatic PE, PE related death, hemodynamic collapse at 30 days (composite measure)
8. Healthcare utilization during hospitalization:
  - a. Time from hospital admission to ICU discharge
  - b. Time from hospital admission to discharge
9. Quality of life (QOL) as measured by the PEmb-QOL and EQ-5D-5L at baseline and 3 month and 12 month post-hospitalization subject follow-up visits
10. IVC filter placement (measured by number of occurrences)

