#### 2 Statistical methods and analysis

#### 2.1 General methodology and definitions

Continuous data will be summarized with means, medians, standard deviations, minima and maxima, unless otherwise specified. Categorical data will be summarized with observed counts and percentages for each category.

All data collected from the eCRF and derived variables will be provided in listings in addition to the summaries described below.

Baseline is defined as the last non-missing assessment prior to the start of APT treatment.

Windowing rules provided below will be used to assign visits to each follow-up assessment for the retrospective and prospective portions of the study. If multiple assessments occur within the same window, the assessment closest to the middle of the "within schedule window" will be used.

Quality of life surveys will be assigned according to the windows: 3 Months (±14 Days) post-APT procedure and 12 Months (±1 Month) post-APT procedure. Echocardiograms will be slotted by month post-APT procedure.

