# 2.7.2 Deaths

Patient deaths will be summarized as all-cause mortality and by cause of death at 30 days, 90 days and through 12-months. A patient listing of all deaths will also be provided.

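### SAP item k puts pulmonary hypertension in 30-day and 365-day windows that do not fit its three-month definition, with no dating rule and no denominator based on who was imaged

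*SAP*

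**What the plan says.** **Windows.** The list in SAP 2.7.1.3 opens with "The following summaries will be provided (within 30 days; within 365 days". Item k is simply "diagnosis of pulmonary hypertension". Other outcomes have time points of their own: item i reads "Major Bleeding Events (within 72 hours; within 30 days; within 365 days", item l is fixed at 30 days, and SAP 2.7.2 says "Patient deaths will be summarized as all-cause mortality and by cause of death at 30 days, 90 days and through 12-months". Item k has none, so it takes the heading's two windows.

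**Definition.** Outcome measure 2 in protocol 5.3 is "pulmonary hypertension defined as mean pulmonary artery pressure greater than 25 mm Hg by echocardiogram that persists at least 3 months after PE diagnosis". The SAP does not restate this.

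**Dating.** SAP 2.1 says only "Echocardiograms will be slotted by month post-APT procedure". The SAP appendix completes partial adverse event dates. Neither says on which date a case of pulmonary hypertension falls.

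**Visits.** The schedule in protocol section 3 gives "3 Months (±14 Days) Post APT (Phone or Visit" and "12 Months (±1 Month) Post APT (Phone or Visit". Echo at both visits is recorded only where it was done. At 3 months it is aimed at patients whose post-treatment echo was abnormal (protocol 5.2 and 10.4). At 12 months it is requested for all (protocol 5.2). For retrospective cases it is whatever the chart holds, up to 12 months (protocol 8.4).

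**Population.** SAP 2.7 places safety analyses on the Safety Population (SP), which SAP 2.2 defines as everyone treated with APT. SAP 2.7 and protocol 13.1 also call for the results by subgroup or treatment protocol. SAP 2.8 carries item k into the periodic summaries.

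**The concern.** A condition that must last three months cannot be confirmed inside 30 days. The 30-day row is therefore either always zero or filled through a back-dating rule that nobody has written down. The 365-day cut raises a related question, because a 12-month visit may take place up to a month later.

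The denominator matters more. The registry's second objective concerns long-term outcomes under different APT regimens, and pulmonary hypertension is one of the listed long-term outcomes. If the table divides cases by all treated patients, anyone without an echo at or after three months is counted as not having the condition. Dose groups, or the retrospective and prospective parts, could then differ because they were scanned at different rates.

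**Working it through.** The documents give no expected rate, scan rate or event count for this outcome, so there is no planned figure to reproduce. The check is calendar arithmetic plus an illustration with assumed inputs.

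**1. The 30-day row.** Three calendar months are 89 to 92 days. SAP 2.7.1.3 does not state day zero; I take it as APT. If PE diagnosis precedes APT by g days, the earliest qualifying day after APT is (89 to 92) − g.
- g = 0: day 89 to 92.
- g = 14 (assumed as an extreme, since eligibility limits symptoms to 14 days): day 75 to 78.
- To reach day 30, g would have to be at least 89 − 30 = 59 days.

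Dated at confirmation, the row is zero. Dated to the first raised echo, it can be filled, but each entry still needs a later echo to confirm it.

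**2. The 365-day row.** With nominal months, the 12-month window is days 335 to 395, or 61 days. Days 366 to 395 are 30 days, and 30/61 = 49% (47% to 52% over actual calendar dates). These are days, not patients. If cases are dated at the confirming echo and visits are spread evenly over the window (both assumed), the share of cases left out is q × 30/61, where q is the share first confirmed at the 12-month echo:
- q = 25%: 12%
- q = 50%: 25%
- q = 100%: 49%

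**3. The 3-month window.** With 3 months taken as day 90, the window is days 76 to 104, or 29 days. Days 76 to 89, which is 14 of the 29, come before three months after APT. If diagnosis was 2 days before APT, it is days 76 to 87, or 12 of 29. No rule says how an echo in this early part counts.

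**4. Denominator, illustration only.** Assume 30% of patients have an abnormal post-treatment echo, with pulmonary hypertension in 10% of those and 1% of the rest. The true rate is 0.30 × 0.10 + 0.70 × 0.01 = 3.7%. Let a and b be the proportions scanned at or after three months among abnormal and other patients.

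SP % = 0.30 × a × 0.10 + 0.70 × b × 0.01

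Imaged-only % = SP % / (0.30a + 0.70b)

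| a / b | SP % | Imaged-only % |
|---|---|---|
| 90% / 60% | 3.1 | 4.5 |
| 80% / 20% | 2.5 | 6.7 |
| 50% / 10% | 1.6 | 7.1 |
| 40% / 40% | 1.5 | 3.7 |

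Two groups with the same true 3.7%, one scanned as in the first row and one as in the third, would show 3.1% against 1.6% on the SP. On the imaged-only base the order reverses: 4.5% against 7.1%.

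**5. What the data alone can say.** Suppose 20 cases among 200 imaged patients out of 500 (assumed). Taking echo readings as correct, the rate lies between 20/500 = 4.0% and (20 + 300)/500 = 64.0%. The upper end is an extreme in which every unimaged patient has the condition.

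**6. Periodic summaries.** With 500 prospective patients enrolled evenly over 24 months (assumed), 500/24 × 3 = 62.5 have not reached three months at a given cut. If all 1000 retrospective cases are in, that is 62.5/1250 = 5.0% of patients at month 12 and 62.5/1500 = 4.2% at month 24.

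**The case against.** The heading in SAP 2.7.1.3 is plainly generic. Item l, fixed at 30 days, does not fit the 365-day half either, and an empty 30-day row misleads few readers. The definition is in the protocol on which the SAP rests, and the SAP also leaves the major bleeding definition there. This lowers the harm of the 30-day row, but it does not supply a dating rule.

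A reader might infer that the day-365 cut loses about half of the 12-month cases. The documents do not support that. It needs a hard cut and dating at the confirming echo; back-dating removes much of the loss. SAP 2.7 speaks of safety through the 12-month follow-up period, which favours counting the whole visit. Retrospective data stop at 12 months, so the issue mainly concerns the prospective patients.

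A reader might also infer that the plan fixes all treated patients as the denominator. It names the SP as the population but no divisor for item k. Protocol 13.11 rules out imputation, and the table shells, held separately, may settle the matter. SAP 2.5 summarises pulmonary arterial pressure from observed data, so numbers measured may be partly visible. That is a summary of the measurement at each time point, however, and not a denominator for the diagnosis. SAP 2.7.3 and 2.7.4 do restrict vital signs and laboratory tests to patients with data; nothing similar is written for item k.

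Finally, in three of the four illustrated scenarios the SP figure is nearer the true rate than the imaged-only figure. That stands, and it is why replacing one denominator with the other would not be enough.

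**Conclusion.** The concern holds in a limited form and should be fixed. The firm part is that item k's 30-day window cannot contain a case dated when protocol 5.3 is met, and the SAP has no rule that would date it otherwise. Conditional on dating at confirmation, 30 of 61 permitted days for the prospective 12-month echo fall outside the 365-day row.

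On the denominator, a percentage of the SP could vary between dose groups or registry parts through scan rates alone. The size and direction of any such effect are not known from the documents; the percentages in the table rest entirely on assumed inputs.

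A smaller point belongs with this one. Protocol 5.3 uses mean pulmonary artery pressure, the echo lists name estimated RVSP, and protocol 13.7 and SAP 2.5 say pulmonary arterial pressure. One might infer that the defining variable is not collected. The schedule's footnote introduces its list as what the echo includes, so the list may not be complete; the naming needs reconciling, and no more can be said.

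These are descriptive registry summaries. No alpha, power or sample size depends on item k.

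**What to change.** Take item k out of the 30/365-day list and give it its own paragraph in the SAP:
- Restate the definition and derive it from echoes at or after three months from PE diagnosis.
- Report at 3 and 12 months, with the full ±1 month window at month 12.
- State how a case is dated, and how echoes in the early half of the 3-month window count.
- Show cases over patients with an evaluable echo beside cases over the SP, with the number not imaged, by dose group and by retrospective and prospective part. Present neither percentage as the true rate.
- In the periodic summaries, restrict item k to patients who have reached three months.
- Reconcile the pressure variable across protocol 5.3, the echo lists, protocol 13.7 and SAP 2.5.

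The cost is SAP wording and table shells. The imaged-only rate has a smaller denominator and a wider interval: with the assumed counts, 20/200 = 10.0% (Wilson 95% CI 6.6 to 14.9) against 20/500 = 4.0% (2.6 to 6.1). There will be two percentages to explain. If the outcome definition itself changes, protocol 15.7 requires an amendment with investigator and IRB/EC approval. A pressure field added now may not recover values never written in retrospective charts.

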## **12.2 Reporting Requirements**

Investigators are not required to report all AEs that occur in the registry.

Investigators must report the following SAEs to Sponsor within one working day of becoming aware of the event for either retrospective or prospective patients. SAEs should be reported up to each subject's 12-month follow-up:

- those related to EKOS or APT procedure
- those related to a bleed
- VTE events

The type of event, severity, and relationship to EKOS, procedure, thrombolytic, and anticoagulation drug will be reported by the Investigator.

Device failures and malfunctions will be reported in the EDC system within one working day after Investigator or delegate learns of the event. For prospective patients, these will also be reported to the relevant IRB/EC as required per IRB/EC requirements.

Because EKOS is a commercially-available medical device, Investigators will comply with any hospital user reporting requirements.

If additional safety information becomes available during the course of the registry, Sponsor will amend the protocol and ICF as necessary.

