### **13.10 Interim Analysis**

Periodic statistical summaries will be prepared annually.

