## **15.8 Suspension or Termination of Registry**

If conditions arise requiring further clarification before the decision can be reached to proceed with or terminate the registry, the registry will be suspended until the situation has been resolved.

Sponsor has the right to terminate this registry at any time. Examples of situations where this might occur include:

- It becomes apparent that enrollment is unsatisfactory with respect to quality and/or quantity or data recording is chronically inaccurate and/or incomplete.
- The incidence and/or severity of adverse events in the registry indicate a potential health hazard caused by the treatment.

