#### 2.8 Interim analysis

Periodic statistical summaries will be prepared semi-annually, to include the following at a minimum:

- Disposition summaries as per section 2.3.1
- Study treatment summaries as per section 2.4.1
- Safety summaries as per section 2.7.1 (2.7.1.3 a, d, i-m) and 2.7.2

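### The SAP plans no summary of SAE severity, so only the frequency half of outcome 5 would be reported, and the thrombolytic and anticoagulant attributions that sites must supply are not tabulated

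*SAP*

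**What the plan says.** **Outcome.** Protocol 5.3, item 5, reads "Frequency and severity of SAEs related to EKOS and procedure, major bleeding, or VTE during index hospitalization and during first 12 months post-APT procedure". Protocol 13.1 promises a summary of every outcome measure, for the whole registry and by APT treatment protocol, with 95% confidence intervals.

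**Collection.** Protocol 12.2 states "The type of event, severity, and relationship to EKOS, procedure, thrombolytic, and anticoagulation drug will be reported by the Investigator". Mandatory SAE reports fall into three classes: related to EKOS or the APT procedure, related to a bleed, and VTE.

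**Analysis.** SAP 2.7.1.3 lists items a to m. Those that matter here are c (related AEs), d (all SAEs), e ("SAEs suspected to be related to procedure and/or device by primary SOC and PT"), h (bleeding), i (major bleeding), j (VTE) and m (fatal AEs). Protocol 13.9 specifies AE and SAE summaries by MedDRA class and term only.

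**Periodic summaries.** SAP 2.8 sets a semi-annual minimum package that includes "Safety summaries as per section 2.7.1 (2.7.1.3 a, d, i-m) and 2.7.2". Protocol 13.10 says "Periodic statistical summaries will be prepared annually".

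**The concern.** Severity is named in the outcome and collected from sites, but then does not appear in the planned tables. Anyone following the SAP as written would report counts for outcome 5 and nothing on how severe the events were.

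The attribution data have a similar gap. The second objective is to describe the effects of varied APT protocols, and SAP 2.2.1 and 2.4.1 classify those protocols by thrombolytic dose. Protocol 4.3 itself links lower dose and shorter treatment to fewer bleeds. Attribution to the thrombolytic therefore bears directly on the comparison of interest, yet no planned table uses it, and the same is true of attribution to the anticoagulant.

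Finally, the minimum periodic package does not guarantee the related-SAE table, and the two documents disagree on how often the package is produced.

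**Working it through.** This is mainly a matter of setting the documents side by side. Only the periodic interval involves arithmetic.

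**1. Outcome 5 against the table list**

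| Component of outcome 5 | Frequency | Severity |
|---|---|---|
| SAEs related to EKOS/procedure | item e | none named |
| Major bleeding | item i | none named |
| VTE | item j | none named |

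Items e and j are produced at 30 and 365 days, and item i also at 72 hours. The frequency column is complete and the severity column is empty. Neither document states a severity scale, so the reported grades would have no common meaning even if they were tabulated.

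**2. Attributions collected against attributions used**

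| Relationship reported (Protocol 12.2) | Used in SAP 2.7.1.3 |
|---|---|
| EKOS | items c, e |
| Procedure | items c, e |
| Thrombolytic | none |
| Anticoagulant | none |

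Restricting e to procedure and device agrees with outcome 5, so it is not a departure from the protocol. The difficulty lies in what counts as procedure. The Intervention row of the protocol synopsis defines the APT procedure as use of the device together with the fluids the physician specifies, which include thrombolytics. Take one serious bleed that the investigator ascribes to the thrombolytic:

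| Site coding | In d | In e | In h | In i |
|---|---|---|---|---|
| Thrombolytic yes, procedure yes | yes | yes | yes | if major |
| Thrombolytic yes, procedure no | yes | no | yes | if major |

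The definition permits the first reading, and the four separate attributions in 12.2 permit the second. Item e therefore depends partly on coding habit, while d, h and i do not.

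**3. Dose bands**

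SAP 2.7 says safety analyses are repeated by the 2.2.1 subgroups. The explicit subgroup list at the end of 2.7.1.3 names only the overall AE summary, all AEs, all SAEs and the most frequent AEs. It names neither related SAEs nor major bleeding, so whether those appear by dose band is left open.

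**4. Periodic package**

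Required: a, d, i, j, k, l, m and deaths. Not required: b, c, e, f, g, h. Item e is a subset of item d, so the package lacks a breakdown but loses no SAEs.

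**5. Periodic interval**

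Inputs: up to 500 prospective patients treated (Protocol 13.2, SAP 2.9) and enrollment over about 24 months (protocol synopsis). The figure of 550 is the number consented, so it is not used here.

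- Rate: 500 / 24 = 20.8 patients per month
- Annual: 500 × 12/24 = 250 newly treated patients between summaries
- Semi-annual: 500 × 6/24 = 125

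These figures assume even accrual to the ceiling and exclude retrospective cases.

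**The case against.** The strongest reply is that little is lost:

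- SAP 2.1 lists all eCRF data, so recorded severity and attributions can be read there.
- The table shells are in a separate document that was not available, and item a could contain a severity row.
- The package in SAP 2.8 is a floor, and more can be added.
- Bleeds are counted in h and i whatever their attribution, so dose bands can be compared without relying on investigator judgement. An SAE attributed only to a drug that is neither a bleed nor VTE need not be reported at all under 12.2, so attribution columns would mostly re-cut events already tabulated.

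The last point stands and limits the value of the attribution tables. The others do not close the gap. A listing is not the summary that Protocol 13.1 promises, an outcome measure should be covered in the SAP itself, and a floor without item e does not guarantee item e.

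A reader might infer more than the documents support:

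- *That outcome 5 cannot be assessed.* Items e, i and j cover its frequency half.
- *That the sponsor could not judge whether to end the registry.* Protocol 15.8 gives as an example "The incidence and/or severity of adverse events in the registry indicate a potential health hazard caused by the treatment". It sets no threshold, and either attribute suffices. Incidence is in the periodic package through d, i, j, l, m and deaths. Individual reports also arrive quickly: "Investigators must report the following SAEs to Sponsor within one working day of becoming aware of the event for either retrospective or prospective patients".
- *That fatal and minor events are indistinguishable.* Item m and SAP 2.7.2 separate deaths, preferred terms separate event types, and Protocol 12.1.6 defines major bleeding by objective criteria.

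**Conclusion.** The point holds as a moderate reporting gap, not as a failure of safety oversight. All three components of outcome 5 lack a planned severity summary and have no stated scale. Two of the four required attributions have no planned table, and because the procedure includes the infused fluid, the content of item e is partly a matter of site coding. How many SAEs that affects cannot be estimated, since the documents give no event rates or attribution shares.

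The periodic interval is a plain contradiction, worth about 250 against 125 prospective patients between summaries under the accrual assumption above. The documents do not show which interval governs. The SAP is written to protocol version 2.0 of 9 May 2018, while the supplied protocol cites a July 2018 publication and may be a later version.

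The conclusion on severity assumes that the unseen table shells do not already contain these tables. If they do, the SAP text still needs to name them.

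**What to change.** 1. **SAP 2.7.1.3, severity.** Add tables of related SAEs, major bleeding and VTE by maximum reported severity per patient, overall and by the 2.2.1 dose bands. State the severity scale.
2. **SAP 2.7.1.3, attribution.** Show SAEs and bleeding events by relationship to EKOS, procedure, thrombolytic and anticoagulant in separate columns, plus one for any of the four. Keep item e unchanged as the outcome 5 definition.
3. **SAP 2.8.** Add item e and the severity table to the minimum set.
4. **Interval.** Reconcile Protocol 13.10 with SAP 2.8, with the sponsor confirming which is current.

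Steps 1 to 3 need SAP wording and a few tables from data Protocol 12.2 already requires. The downside is slightly longer output. If the scale was never given to sites, grades already reported may not be comparable, and the report should say so. Step 4 is an SAP edit if the annual interval stands. If the protocol has to change, Protocol 15.7 requires approval by the investigator, sponsor and IRB/EC, at up to 100 sites, so that edit is best bundled with another amendment.

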## 10.4 Follow-Up

Patients will be followed per Investigator's SoC for up to 12 months post-APT procedure. At 3 months and 12 months post-APT procedure, the following data should be recorded, as

available. For patients with an abnormal post-treatment echocardiogram, a 3-month follow-up echocardiogram is recommended to assess for chronic pulmonary hypertension. For other patients, 3-month data can be collected via phone or on-site visit.

- Echocardiogram: RV/LV ratio, TAPSE, estimated RVSP, and the collapse of the IVC with respiration
- Review any SAEs, hospitalizations. Record any SAEs related to occurrence of VTE or bleeding events
- Review any changes in anticoagulation medications
- Quality of Life surveys: PEmb-QOL and EQ-5D-5L
- In case of mortality, review cause and time of occurrence
- In case of withdrawal, review cause and time of occurrence

If additional echocardiogram(s) are collected outside of the 3 and 12 month follow-up, the results should be recorded in the EDC.

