### **13.9 Safety Analyses**

Safety analyses will be conducted on the SP during hospitalization and through the 12-month follow-up period. AEs and SAEs will be summarized by MedDRA System Organ Class and Preferred Term.

In addition, occurrence of safety outcomes will be summarized, including diagnosis of pulmonary hypertension, all-cause mortality during first 12 months, composite measure of recurrent symptomatic PE, PE related death or hemodynamic collapse at 30 days.

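### SAP 2.7.1.3 tabulates all AEs and all SAEs as percentages of treated patients, but protocol 12.2 requires only three classes of event, so these percentages are floor values under titles that imply completeness

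*SAP*

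**What the plan says.** **Capture.** Protocol 12.2 opens with "Investigators are not required to report all AEs that occur in the registry". It continues: "Investigators must report the following SAEs to Sponsor within one working day of becoming aware of the event for either retrospective or prospective patients". The list has three entries: "those related to EKOS or APT procedure", "those related to a bleed", and VTE events.

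Other capture sections have a similarly limited scope:
- Protocol 10.4 (prospective follow-up) has sites review SAEs and hospitalizations, but the recording instruction is "Record any SAEs related to occurrence of VTE or bleeding events".
- Protocol 8.3 (retrospective, in hospital) lists related SAEs, bleeding events and VTE events.
- Protocol 8.4 (retrospective, long term) lists VTE or bleeding events, with mortality as a separate item, all as available.

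**Tabulation.** SAP 2.7.1.2 bases the summaries on every treatment-emergent AE and reports counts and percentages of patients. SAP 2.7 assigns the safety analyses to the safety population, which SAP 2.2 defines as everyone who receives the APT procedure. SAP 2.7.1.3 then lists, within 30 and 365 days, an overall AE summary (a), "All AEs by primary SOC and PT" (b), AEs related to procedure or device (c), SAEs without restriction (d), AEs leading to discontinuation (f) and "Most frequent AEs (5% or 10%) by primary SOC and PT" (g). Items a, b, d and g are named again for the subgroups of SAP 2.2.1: dose band, PE severity, region and registry portion. Protocol 13.9 is equally unrestricted: "AEs and SAEs will be summarized by MedDRA System Organ Class and Preferred Term".

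Neither document limits these tables to the reportable classes or adds a caveat.

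**The concern.** An incidence table needs a numerator collected as completely as its denominator. Here the denominator is every treated patient, while the numerator for most AE terms is whatever was entered without a duty to enter it. A reader who sees a title covering all AEs or all SAEs over 365 days will take the percentage as the registry's safety incidence. It is a lower bound.

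The frequency threshold is the weakest item. Whether a non-reportable term passes 5% or 10% depends on reporting habit as well as on how often the event happens. A term missing from that table would be read as uncommon when it may only be unreported.

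One registry objective is to describe the effects of varied APT protocols on long-term outcomes, and the subgroup versions put these same percentages side by side across dose bands. SAP 2.8 also carries items a and d into the periodic summaries, so the titles would recur before the final report.

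**Working it through.** The documents state no AE rate, so there is no plan figure to reproduce. The main check sets each SAP 2.7.1.3 item against the reporting duty in protocol 12.2.

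| SAP item | Content | Within the required classes? |
|---|---|---|
| a | Overall AE summary | Partly |
| b | All AEs | Partly |
| c | Related AEs, serious and non-serious | Serious part only |
| d | All SAEs | Partly: related and bleed-related SAEs, and VTE |
| e | Related SAEs | Yes |
| f | AEs leading to discontinuation | Partly |
| g | AEs above 5% or 10% | Partly |
| h | All bleeding events | Serious bleeds; non-serious bleeds not clearly required for prospective patients |
| i | Major bleeding | Yes, in substance |
| j | VTE | Yes |
| l | 30-day composite | Recurrent PE as VTE; hemodynamic collapse is not a named class |

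All-cause mortality (SAP 2.7.2) is collected separately under protocol 8.4 and 10.4 and is outside the problem.

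**Direction.** Take at most one event of a given kind per patient. Let q be the share of such events that fall in the required classes, and v the probability that any other event is reported anyway. Then

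tabulated incidence = true incidence × [q + (1 − q) × v].

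The bracket never exceeds 1. It equals 1 only if q = 1 or v = 1. The tabulated figure is therefore at or below the truth.

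**Illustration.** The values of q and v and the true rate of 10% are assumptions; none is in the documents.

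| q | v = 0 | v = 25% | v = 50% | v = 100% |
|---|---|---|---|---|
| 0 | 0% | 2.5% | 5% | 10% |
| 50% | 5% | 6.25% | 7.5% | 10% |

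For example, with q = 0 and v = 25%: 0.10 × [0 + 1 × 0.25] = 2.5%. With q = 50% and v = 25%: 0.10 × [0.5 + 0.5 × 0.25] = 6.25%.

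**The 5% or 10% cut.** Use 500 patients, the prospective target, so 5% is 25 patients and 10% is 50. For a term with true incidence 10% and q = 0, the number reported is binomial(500, 0.10 × v). The chance of reaching 25 is:
- v = 25%: 0.1%
- v = 40%: 15%
- v = 50%: 53%
- v = 75%: 99%

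The chance of reaching 50 is 52% under full reporting and about 0% at v = 50%. The same clinical reality can put a term in or out of item g on reporting alone.

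**The case against.** The strongest replies are these.

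1. *The assessment schedule has a row for adverse, VTE and bleeding events, so full capture may be intended.* The row does not say which AEs to record and cannot override the explicit rule in protocol 12.2.

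2. *The EDC may accept only the required classes, so nothing is reported unevenly.* The documents do not settle this. If it is so, v = 0 and the all-AE and all-SAE tables hold only the required classes. The defect is then mainly one of title and scope, but the titles are still wrong.

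3. *The registry is descriptive, no test is planned on AEs, and all AEs are listed anyway.* This limits the harm. A descriptive percentage still needs a complete numerator or an honest label.

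Three stronger readings are tempting and are not supported.

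- *That bleeding, VTE, related SAEs and the composite are left out of the subgroup analyses.* The short list in SAP 2.7.1.3 does not name them. However, SAP 2.7 says safety analyses will also be given by the SAP 2.2.1 subgroups, SAP 2.2.1 says the same of safety outcome measures, and protocol 13.1 promises each outcome measure by APT protocol, PE severity, region and portion. The short list needs reconciling with these; it does not prove an omission.

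- *That differences between dose bands or regions will reflect which sites volunteer events.* The arithmetic allows it: a common true incidence of 20% with q = 0 would show as 0.20 × 0.25 = 5% in one group and 0.20 × 0.75 = 15% in another. But nothing in the documents shows that sites report voluntarily, or that such reporting differs by subgroup. It is a possibility only.

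- *That SAE rates are understated by some stated fraction.* The documents give neither the share of SAEs in the required classes nor any SAE rate.

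**Conclusion.** The mismatch is real and follows from the documents alone. Items a, b, d, f, g and the non-serious part of c are planned as percentages of all treated patients, although the events behind them need not all be reported. The direction is certain: these percentages are floor values. The size cannot be computed from the documents; the figures above rest on assumed values of q, v and the true rate, and show only how the mechanism works. Uneven reporting between sites is possible but undocumented.

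Items e, i and j rest on required reports and can stand as incidence tables. Items h and l need a statement of how their non-required components are found. The plan should be corrected before the tables are produced, but its core safety outcomes remain usable.

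**What to change.** In SAP 2.7.1.3:
- Restrict items a and d to the SAEs reportable under protocol 12.2 and say so in the titles.
- Present b, f, g and the non-serious part of c as listings of reported events, with a note that such AEs were not systematically collected. Drop the 5% or 10% threshold.
- Apply the same restriction to the subgroup versions and to the periodic summaries in SAP 2.8 that use a and d.
- Reconcile the short subgroup list with SAP 2.7 and 2.2.1 by naming related SAEs (e), major bleeding (i) and VTE (j) explicitly.
- State how non-serious bleeding in h and hemodynamic collapse in l are ascertained.

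Align the wording of protocol 13.9 with 12.2. All-cause mortality in SAP 2.7.2 needs no change.

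The cost is SAP, table-shell and protocol wording edits, with no new data collection. The downside is fewer AE tables.
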